	Screening (prior t	Day -10	24-48 hours t Day -10							-	Trea	tmer	nt Pe	riod							-	Follow-up post-la	Follow-up after last do	Notes
Procedure	Screening (up to 45 Days prior to Day 1)	Day -10 $(\pm 3 \text{ days})$		Day -1	Day 1	Day 2	Day 3	Day 4	Day 5	Day 6	Day 7	Day 8	Day 9	Day 10	Day 11	Day 12	Day 13	Day 14	Day 15	Day 16	_	Follow-up 1 (7-14 days post-last dose)	Follow-up 2 (5 weeks after last dose \pm 3 days)	The 2nd follow up visit is only required for those participants where challenges are being administered and blisters induced
Visual forearm check (including blister healing and cosmetic assessment)	x	х		x													x					Х	x	Pre-cantharidin check to be within three hours prior to cantharidin application. See Section 2.4.2 and Section 2.4.3 for further details of timing of forearm checks on Day 13, 14, 15 and 16 in relation to challenges.
AE / SAE review	SA	Es coll	ected f	rom	signi			orme 1 time											AEs	collect	ted	continu	iously	
Concomitant Medication Review					N							n firs		se ur					treat	ment				
Treatment / agent a	Idminis	tratio	1		-																			
Study Drug Administration					х	Х	Х	Х	х	Х	Х	Х	Х	Х	Х	Х	Х	Х						Once-daily in the morning on Days 1-14 inclusive.
Cantharidin application		х																Х						Day – 10: to be applied in the morning. See Section 2.4.2 and Section 2.4.3 for further details on Day 14 blister timings.
In vivo LPS or GM- CSF Challenge																		Х						See Section 2.4.1 for further details.
Pharmacokinetics, I	Pharma	codyı	namics	and	Ge	netio	cs S	ampl	e															
Blood sampling for systemic PK [S1] and [S2]					x	x		x				x				x		x	x	x				On Day 1 samples will be taken at pre-dose, 15mins, 30mins, 1h, 2h, 4h, 6h, 8h, 12h and 24h post-dose, Pre-dose samples Days 4, 8 and 12. See Section 2.4.1 for Day 14, 15 and 16 sample timings. Ad-hoc sample to be taken in the event of any cardiac arrhythmias, as close as possible to the time of occurrence
Blood sampling for intracellular PK [S3]					х			х				х				х	х	x	x	х				On Day 1 and Day 13 samples will be taken at 1h, 4h and 8h post-dose. Pre-dose samples Days 4, 8 and 12. See Section 2.4.1 for Day 14, 15 and 16 sample timings.

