Urine sample for metabolite analysis [E4]					x	x												x	x					A 0-24 urine collection will be made on Day 1 and Day 14. In each case, for the pre-dose sample, immediately prior to dosing participants will be instructed to void their bladder into a collection container. Following dosing participants will be instructed to collect all urine voided for a 0-24 hour collection.

2.4.1. Part C Day 14 Detailed SoA for Challenge Administration and PK Sampling Cohorts 4 and 8 (with challenges)

Procedure	Day 13	Pre-dose	Day 14 relatio		dose an he adm 30 mins						in 12 h	Day 15 24 h	Day 16 48 h	Notes
Treatment / agent administration	on and P	K sam	npling									-		
Study Drug / Placebo Administration			Х											
In vivo LPS Challenge					< =:					== >				LPS administration may be performed at low systemic GSK3358699 concs when intracellular levels of GSK3206944 are high; the decision on the timepoint will be based on emerging data and will be no more than 24hrs after dosing on Day 14.
OR in vivo GM-CSF Challenge					< ==		=====	=====			= >			GM-CSF administration may be performed at low systemic GSK3358699 concs when intracellular levels of GSK3206944 are high; the decision on the timepoint will be based on emerging data. GM-CSF will be administered as an infusion over 2 hours and the start of the infusion will be no more than 24hrs after dosing on Day 14.
Blood sampling for systemic PK [S1] and [S2]		Х		Х	Х	Х	Х	Х	Х	Х	Х	х	Х	Ad-hoc sample to be taken in the event of any cardiac arrhythmias, as close as possible to the time of occurrence
Blood sampling for intracellular PK [S3]	Х					х		х		х		х	Х	Pre-challenge samples. To be collected only until the start of challenge administration
Blood sample for ex vivo PD assay [S4]	х	х				x		x		x		x		Pre-challenge samples. To be collected only until the start of challenge administration.
Blood sample for circulating proteins [E1a]		х					х	х		х		х		Pre-challenge samples. To be collected only until the start of challenge administration.
Blood sample for gene panel [E1b]		х					х	x		х		х		Pre-challenge samples. To be collected only until the start of challenge administration.
Cantharidin application and PD sampling					See S	ection	2.4.2 a	and Se	ction 2	.4.3				

2.4.2. Part C Day 14 Detailed SoA for LPS Challenge and Biomarker Sampling Cohorts 4 and 8 (with challenges)

Procedure	Day 13				and all							Day 15	Day 16	
Tiocedure	13	Pre-dose	0 h	20 mins	1 h	2 h	3 h	4 h	6h	8 h	12 h	24 h	48 h	Notes

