LPS challenge administration			х											See Section 2.4.1 for timing of LPS administration in relation to GSK3358699 / placebo dose.
Visual forearm check (including blister healing and cosmetic assessment)	х	х										х	х	Pre-cantharidin check to be within three hours prior to cantharidin application.
Cantharidin application				Х										To be applied 20 minutes post LPS challenge.
Intravenous hydration with normal Saline at a rate of 250 mL / hr		<==		=====				=====	=====	===>				From 4 hours prior to LPS challenge administration until 8 hours after LPS challenge administration.
Vital Signs	x	x	<==		=====						===>	x	x	BP, HR, temperature, respiratory rate. Pre-dose vital signs to be taken pre-LPS challenge administration then post-LPS challenge as follows: every half hour for the first 4 hours, hourly until 12 hours, then 6-8 hourly until discharge. Frequency can be increased if symptomatic.
Haematology	Х								Х		Х	Х	Х	
Coagulation	Х							Х						
Blood sample for circulating inflammatory biomarkers [E2a]		х			х	Х	Х		Х			Х	Х	
Blood sample for cellular activation markers [E2b]		х			х				х			х	х	
Blood sample for gene panel [E2d]		х			х		х		х			х		
Blister sample for biomarkers, blister volume and cell counts [E3]													х	Blisters harvested approx 48 h post cantharidin application.

2.4.3. Part C Day 14 Detailed SoA for GM-CSF Challenge and Biomarker Sampling Cohorts 4 and 8 (with challenges)

	Da	Day			and all GM-CS							start	Day 15	Day 16	Notes
Procedure	Day 13	Pre-dose	0 h	1 h	2 h	2h 20mins	3 h	4 h	5h	6 h	8 h	12 h	24 h	48 h	
GM-CSF challenge administration			<==		===>										See Section 2.4.1 for timing of the start of the GM-CSF infusion in relation to GSK3358699 / placebo dose. GM-CSF will be administered as an infusion over 2 hours.
Visual forearm check (including blister healing and cosmetic assessment)	x			х									x	х	Pre-cantharidin check to be within three hours prior to cantharidin application.
Cantharidin application						Х									2 hours and 20 minutes after the start of the GM-CSF challenge.
Vital Signs	x	х	<=:									==>	x	х	BP, HR, temperature, respiratory rate. Pre-dose vital signs to be taken pre-GM-CSF challenge administration then post-GM-CSF challenge as follows: every half hour for the first 4 hours, hourly until 8 hours, then 6-8 hourly until discharge. Frequency can be increased if symptomatic.
Haematology	Х							Х			Х		Х	Х	

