- In vivo GM-CSF challenge GM-CSF has a broad range of activities across innate and adaptive immune cells and is recognised as a key mediator in a number of inflammatory diseases, such as arthritis, multiple sclerosis, colitis, pain and interstitial lung disease [Wicks et al 2016]. Leukine (Sargramostim) given intravenously results in a systemic GM-CSF challenge that mobilises neutrophils, eosinophils and monocytes from the bone marrow. A GM-CSF dose of 5 µg/kg (equivalent to intravenous infusion of 60 µg/m²), administered subcutaneously, is associated with a measurable leukocyte response but is well tolerated based on the literature [Gianni et al 1990, Lieschke et al 1989]. 1.5µg/kg dose infused intravenously over 2 hours provides the same exposure (AUC) due to the increased bioavailability and higher C_{max} concentrations (Cebon et al 1990). This study will investigate the effect of GSK3358699 on GM-CSF induced inflammation as measured by leukocyte numbers, soluble inflammatory mediators, as well as cellular activation markers on leukocytes, particularly monocytes, over a defined time course.
- Chemically induced skin blisters Cantharidin is a vesicant (an agent that causes blisters) and a strong inhibitor of protein phosphatases type 1 and 2A [Honkanen et al 1993], used clinically for the treatment of warts and molluscum contagiosum. Following contact with the skin, it is absorbed into the epidermis and activates proteases leading to intra-epidermal blistering [Bertaux et al 1988]. Blistering is limited to the suprabasal epidermis and lesions heal without scarring. Skin blister induction by cantharidin has been utilised in clinical pharmacology for more than 50 years as a model of acute inflammation, and provides methodology to investigate leukocyte trafficking, cellular activation states and detection of plethora of inflammatory mediators, including pro-fibrotic mediators, in the blister fluid. The combination of blisters with systemic inflammation (induced by LPS or GM-CSF) provides a unique methodology to detect the effects of systemic inflammation on local inflammation. This study will investigate the effect of GSK3358699 on cantharidin induced blisters in the presence of systemic inflammation, as measured by leukocyte numbers, cellular activation markers and soluble inflammatory mediators associated with autoimmune and fibrotic diseases.

This study will be conducted in healthy male participants for the following reasons:

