10. STATISTICAL CONSIDERATIONS

10.1. Hypotheses

As the primary objective of the study is to assess the safety of GSK3358699 in healthy volunteers, there are no formal hypotheses. There are also no formal hypotheses to be tested for the single or repeat dose PK data.

An estimation approach will be used to quantify the single dose PK for each dose level studied, the food effect and also to assess PK parameters following 14 days repeat dosing relative to single dosing.

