5.2. Study Treatment Display Descriptors

In the Tables, Listings and Figures (TLF), treatment should be presented with placebo first, then in order of increasing dose within each part.

Part A	Part A: Treatment group descriptions				
Rand	andAll NG Data displays for reporting				
Code	RandAll description	Table/FigureListing LabelOrder in T		Order in TLF	
		Label			
А	1 mg GSK3358699 SD	1 mg SD	1 mg SD – A	2	
В	3 mg GSK3358699 SD	3 mg SD	3 mg SD – B	3	
С	10 mg GSK3358699 SD	10 mg SD	10 mg SD – C	4	
D	20 mg GSK3358699 SD	20 mg SD	20 mg SD – D	5	
Е	35 mg GSK3358699 SD	40 mg SD	40 mg SD – E	8	
F	45 mg GSK3358699 SD	30 mg SD	30 mg SD – F	7	
R	Dose X GSK3358699 SD	25 mg SD	25 mg SD – R	6	
P Placebo SD		Placebo SD	Placebo SD – P	1	
Note: doses in RandAll descriptions and display descriptions differ for treatments E, F, R					
due to DEC decisions.					

Part C: Treatment group descriptions					
RandAll NG		Data displays for reporting			
Code	Description	Table/Figure Label	Listing Label	Order in TLF	
Ι	Dose 1 GSK3358699 RD	10 mg RD	10 mg RD - I	2	
J	Dose 2 GSK3358699 RD	10 mg RD	10 mg RD - I	2	
QPlacebo RDPlacebo RD - Q			1		
Note: the same dose level was administered in both Cohorts 4 and 5 due to the early					

Note: the same dose level was administered in both Cohorts 4 and 5 due to the early termination of Cohort 4. Subjects in the active treatment group from both cohorts will be summarised and listed under the same treatment label.

207546

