9.1.3. Summary Measure

In addition to the parameters mentioned above, the following will also be calculated:

Part C	(repeat dose)
R ₀	• Accumulation between 1 single dose (Day 1) and repeat dose (Day 14)
	• Calculated as R0 =AUC(0-tau) Day 14/AUC(0-tau) Day 1
Rs	• Steady state ratio (time invariance kinetics)
	• Calculated as Rs=AUC(0-tau) Day 14/AUC(0-inf) Day 1

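### In the challenge cohorts the Day 14 plasma profile runs through the LPS or GM-CSF challenge, and the SAP has no rule for keeping challenged profiles out of R0, Rs and the pooled 10 mg summary

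*Protocol*

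**What the plan says.** **Sampling in Cohorts 4 and 8.** In Protocol 2.4.1 the Day 14 rows for intracellular PK (S3), ex vivo PD (S4), circulating proteins (E1a) and gene panel (E1b) carry the note "Pre-challenge samples. To be collected only until the start of challenge administration". The plasma PK row (S1/S2) is marked from pre-dose to 48 h, and its only note concerns an ad-hoc sample after an arrhythmia. The LPS challenge "will be no more than 24hrs after dosing on Day 14"; the same limit applies to the start of the GM-CSF infusion.

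**Profile before the challenge.** For intracellular PK, Protocol 2.4 states "On Day 1 and Day 13 samples will be taken at 1h, 4h and 8h post-dose", and the S4 row has matching Day 13 samples. Plasma PK has no Day 13 samples. Protocol 6.3.1 names Days 1 and 14 as the full PK profiling days.

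**Analysis.** Protocol 10.1 sets out to quantify single-dose PK and "also to assess PK parameters following 14 days repeat dosing relative to single dosing". SAP 9.1.3 defines the accumulation ratio: "Calculated as R0 =AUC(0-tau) Day 14/AUC(0-tau) Day 1". Rs has the same numerator. On the two 10 mg cohorts, SAP 5.2 says "Subjects in the active treatment group from both cohorts will be summarised and listed under the same treatment label". SAP 13.6.1 excludes PK data collected after each cohort's termination date from summaries. The SAP has no corresponding rule for samples taken after a challenge.

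**Part A.** In the SAP 2.3 sequences, code R (25 mg) appears only in the fourth position, which is the challenge period. Protocol 5.1.1.2 places that challenge at the parent's systemic Cmax. SAP 5.2 labels the dose simply 25 mg SD, and the power model in SAP 9.1.5.1 has neither a challenge term nor an exclusion.

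**The concern.** R0 is meant to compare a repeat-dose profile with a single-dose profile in the same person. In a challenged participant the Day 14 profile differs from Day 1 in two ways: it follows repeat dosing, and it contains an inflammatory challenge. The ratio cannot separate them.

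The protocol gives some reason to take the second difference seriously. Section 3 says the parent is hydrolysed by CES-1 in mononuclear-myeloid cells and hepatocytes. Section 5.4 says intravenous GM-CSF "mobilises neutrophils, eosinophils and monocytes from the bone marrow" and that LPS challenge changes leukocyte numbers. LPS participants also receive saline at 250 mL/h "From 4 hours prior to LPS challenge administration until 8 hours after LPS challenge administration", which is 12 h × 250 mL/h = 3 L. Day 1 has none of this.

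At stake is a stated estimation aim. The predicted R0 is close to 1, so a modest shift from the challenge could be read as accumulation or as time-dependent kinetics. The shared label would hide where it came from: the SAP 5.2 listing label is also identical for the two cohorts.

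**Working it through.** The documents state no accumulation ratio or challenge effect, so there is no figure to reproduce. The check has three parts.

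**1. Rows side by side (Protocol 2.4 and 2.4.1, Cohorts 4 and 8)**

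| Sample | Stops at challenge start? | Day 13 post-dose profile? |
|---|---|---|
| S3 intracellular PK | yes | yes |
| S4 ex vivo PD | yes | yes |
| E1a, E1b | yes | no |
| S1/S2 plasma PK | no | no |

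With once-daily dosing tau is 24 h, so a challenge at or before 24 h falls within the dosing interval or at its end.

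**2. How much of the AUC could be affected**

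Inputs for the parent: half-life about 3 h (Protocol 5.4), and predicted Cmax 42 ng/ml with AUC 255 ng/ml.h at 45 mg (Protocol 5.5.1). Assumption: a one-compartment oral model, with the absorption rate solved so that Cmax/AUC = 42/255.

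- k = ln 2 / 3 = 0.231 per h; ka = 1.51 per h; tmax about 1.5 h.
- Expected ratio from repeat dosing alone: 1/(1 − 2^−8) = 1.004, so R0 should be about 1.00.
- Fraction of total AUC after time t: F(t) = [ka·e^(−kt) − k·e^(−ka·t)] / (ka − k).
- Share of AUC(0-24) after a challenge at t: s = [F(t) − F(24)] / [1 − F(24)].
- At 12 h: F(12) = 0.0738 and F(24) = 0.0046, so s = 0.0692/0.9954 = 7%.

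If clearance is multiplied by m from the challenge onward and absorption is nearly complete, then R0 ≈ 1 + s·{[(1 − e^(−mk(24−t)))/m] / [1 − e^(−k(24−t))] − 1}. At 12 h with m = 0.5 this is 1 + 0.069 × (1.5/0.9375 − 1) = 1.04.

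| Challenge at | Share of AUC(0-24) after it (half-life 2.5–4 h) | R0 if clearance ×0.5 / ×0.7 / ×1.5 |
|---|---|---|
| 24 h | 0% | 1.00 / 1.00 / 1.00 |
| 12 h | 7% (5–11%) | 1.04 / 1.02 / 0.98 |
| 8 h | 18% (16–24%) | 1.13 / 1.07 / 0.94 |
| 4 h | 47% (46–50%) | 1.38 / 1.18 / 0.85 |

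The clearance multipliers are purely illustrative, because the documents give none. The model covers the parent only. The documents give no plasma half-life for the acid metabolite.

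**3. Part A dose proportionality**

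Use the actual doses 1, 3, 10, 20, 30 and 40 mg with six active profiles each, plus 12 planned at 25 mg (six per cohort in Period 4). Apply ordinary least squares on log dose, ignoring the participant effect.

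- Mean log dose = 119.55/48 = 2.491; sum of squares = 70.5.
- A shift of δ in every 25 mg log value moves the slope by 12 × (3.219 − 2.491) × δ / 70.5 = 0.124δ.
- +20%: δ = 0.182, so the slope moves from 1.00 to 1.02. −20%: δ = −0.223, so it moves to 0.97.

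The slope is therefore insensitive. The 25 mg descriptive row would carry the whole shift.

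**The case against.** Several points on the other side are sound.

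- **Timing.** Protocol 2.4.1 and 5.4 say the Part C challenge may be given when plasma parent is low and intracellular acid is high. With a 3 h half-life that points to later times, where the table shows little or no effect. The wording is permissive, so earlier timing is not ruled out, but it is not the stated intention.
- **Cohort 4 may contribute nothing.** Protocol 5.1.3.1 says it was started but not completed. SAP 13.6.1 gives a termination date of 14 November 2018, with some participants part way through treatment. Cohort 8 was never dosed (SAP 2.3). A reader might infer from the planned active numbers (ten in Cohort 4, nine in Cohort 5) that about half the pooled ratios are challenged. The documents do not support that: they do not say whether any challenged Day 14 profile exists.
- **No stated mechanism.** Nothing in either document says that LPS, GM-CSF or saline alters plasma PK. Protocol 5.5.4 builds the human PK model on hepatic and renal clearance. Section 3.3.1 calls the drug a weak CYP3A4 inhibitor but does not say CYP3A4 clears it, so an argument from auto-inhibition would be speculative.
- **The unequal sampling limits have a plausible reason.** S4 and E1 are direct inflammatory readouts, whereas a plasma concentration is not. Protocol 5.4 wants systemic and intracellular exposure related to the challenge response, which needs post-challenge plasma samples.
- **Unchallenged evidence exists.** Cohort 5 has the same Day 14 plasma profile without challenge. The pre-dose samples on Days 4, 8, 12 and 14 precede any challenge.

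These points limit the size and rule out cutting the sampling short. They do not supply the missing analysis rule. Cohort 5 gives an unchallenged R0 only if it is not pooled with challenged profiles, and SAP 5.2 pools the two cohorts.

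**Conclusion.** The point holds as a gap in the analysis rules. As written, the SAP would put any challenged Cohort 4 profile into R0, Rs and the pooled 10 mg Day 14 parameters without a flag, and accumulation could not then be separated from the challenge.

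The effect is possible, not demonstrated, and its size and direction are unknown. Under the one-compartment assumption it is small for a late challenge (about 7% of AUC(0-24) lies after 12 h). It is nil at 24 h, and nil if no Cohort 4 participant was challenged before termination. A reader might conclude that the reported R0 is biased, or that the protocol was wrong to keep sampling plasma after the challenge. The documents support neither conclusion.

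In Part A every planned 25 mg profile comes from the challenge period. The power-model slope barely depends on it, but the 25 mg row should say so.

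**What to change.** **SAP 9.1.3 and Table 3.9.** State that R0, Rs and the pooled 10 mg Day 14 parameters use only profiles with no LPS or GM-CSF challenge inside the dosing interval. List or summarise challenged profiles separately by cohort, with the challenge time. If there are none, say so.

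**Part A.** In Table 3.4 label the 25 mg (Period 4) row as given with LPS/GM-CSF challenge. In Table 3.5, if the power model is fitted, show the slope with and without the 25 mg data.

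**Sampling.** Keep the Day 14 post-challenge plasma samples. For any future challenge cohort, consider a plasma profile on the day before the challenge. A fixed Day 13 would not suit a cohort that may be dosed for fewer than 14 days. Using the volumes in Protocol 9.5.1, this adds seven samples of 1 mL (pre-dose to 6 h) and two of 2 mL (8 h and 12 h), or 11 mL in all. The 24 h sample is the next day's existing pre-dose draw. The post-dose fast should match the 4 h used on Day 1.

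**Cost.** A few SAP sentences and one label, with fewer participants in the main R0 summary if any Cohort 4 profile was challenged. While editing, reconcile Rs, whose denominator is Day 1 AUC(0-inf), with SAP 9.1.2, which calculates that parameter for Part A only.

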3. INTRODUCTION

GSK3358699 is a targeted inhibitor of the bromodomain and extra-terminal domain (BET) family of epigenetic reader proteins [Ferri et al 2016, Chung et al 2012, Filippakopoulos et al 2014]. Recent literature reports have demonstrated that inhibitors of this protein family profoundly affect many of the pro-inflammatory molecular and cellular mechanisms which underpin a multitude of immuno-inflammatory diseases [Nicodeme et al 2010, Mele et al 2013, Klein et al 2016]. To date, however, the clinical evaluation of panBET inhibitors such as GSK525762 [Mirguet et al 2013] has centred on oncology, with no reports citing the use of this pharmacology outside malignant neoplastic diseases [Jung et al 2015, Belkina et al 2012, Yu et al 2015, Dawson et al 2012]. With a view to further exploring the potential of BET family inhibition in human disease, GlaxoSmithKline (GSK) is developing GSK3358699, a mononuclear myeloid targeted BET inhibitor. Based on pre-clinical work to date GSK3358699 has the potential to effect positive outcomes in myeloid-centric diseases with unmet need; including but not limited to rheumatoid arthritis (RA), psoriasis, fibrotic liver disease and inflammatory bowel disease (IBD), with the potential to provide an improved safety profile compared to other panBET inhibitors [GlaxoSmithKline Document Number 2017N333959 00].

In contrast to conventional inhibitors of the BET proteins and unique within this target class, GSK3358699 encompasses within its chemical structure an Esterase Sensitive Motif (ESM) [Needham et al 2011]. This cell targeting technology enables preferential delivery of the BET pharmacology to cells expressing human carboxyesterase-1 (*CES*-1), thereby limiting less desirable systemic effects. These target cells are primarily those of the mononuclear-myeloid lineage, including monocytes, macrophages and dendritic cells, but also include hepatocytes.

More specifically, GSK3358699 is selectively hydrolysed by the esterase *CES*-1 in target cells to form a pharmacologically active carboxylic acid, GSK3206944. Like GSK3358699, this acid metabolite is a potent BET inhibitor, which, because of its charged nature, is selectively retained in high local concentrations within mononuclear myeloid cells.

Targeting inflammatory cells that are sensitive to BET inhibition and play a key role in many inflammatory diseases [Chan et al 2015] should reduce non-target side effects leading to a wider therapeutic window relative to conventional non-targeted BET inhibitors. As a result, GSK3358699 has the potential to become a novel and important therapeutic modality for the treatment of inflammatory and fibrotic disorders.

